4.2 Exclusion Criteria

Patients who meet any of the following exclusion criteria will not be eligible to participate in the study:

1. Have participated in another clinical trial within the last year where patient received active treatment for NASH.
2. Have participated in a clinical trial for any other indication within the last 3 months or 5 half-lives of the treatment, whichever is longer.
3. Have participated in another Corcept study with miricorilant.
4. Women who are pregnant, planning to become pregnant, or are lactating.
5. Have a BMI <18 kg/m².
6. Are currently using any medications prohibited due to the potential for drug-drug interactions (DDI) with study treatments Prohibited medications (see Section 5.4.3) must be discontinued at least 5 half-lives prior to a patient receiving their first study treatment. Administration of concomitant medications (see Section 5.4) are at the discretion of the Investigator and/or the Corcept Medical Monitor.
7. Have had successful weight-loss surgery prior to Screening or are planning weight-loss surgery during the study*.

*Patients who have had Roux-en-Y gastric bypass surgery or other surgical procedures that have a fundamentally altered gastrointestinal tract may not participate regardless of success of the procedure.

8. Have any elective surgery planned during the study.
9. Have significant alcohol consumption, defined as more than 2 drink units per day (equivalent to 20 g of ethanol) in women and 3 drink units per day (equivalent to 30 g of ethanol) in men for ≥ 3 consecutive months within 1 year prior to Screening, inability to reliably quantify alcohol intake, or score a value ≥ 8 on the Alcohol Use Disorders Identification Test (AUDIT) questionnaire.
10. Use of drugs associated with NAFLD (e.g., amiodarone, methotrexate, oral or intravenous GCs, at supraphysiological doses (prednisone equivalent ≥ 5 mg/day), tamoxifen, estrogens at doses greater than those used for hormone replacement or contraception, anabolic steroids, or valproic acid) for more than 4 weeks in the 2 months prior to randomization.
11. Have been treated with obeticholic acid, ursodeoxycholic acid (Ursodiol[®] and Urso[®]), pioglitazone or high-dose vitamin E (>400 IU/day) within the 3 months prior to Screening imaging studies.
12. Have had liver transplantation or plan to have liver transplantation during the study.
13. Have type 1 diabetes.
14. Have type 2 diabetes and:
 - a. An HbA1c $\geq 9.5\%$

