5.3.3 Dose Interruption and/or Discontinuation: Special Safety Events

Based on the mechanism of action of miricorilant, there is a theoretical risk of excessive GR antagonism and excessive MR antagonism. Thus far in clinical experience with miricorilant in healthy volunteers as well as in patients with AIWG, an increased incidence of excessive GR or MR antagonism has not been observed. Excessive GR antagonism could manifest as a combination of findings such as weakness, tiredness, dizziness, orthostatic hypotension, hypoglycemia, dehydration, nausea, vomiting, diarrhea, and muscle aches. Excessive MR antagonism could manifest as hyperkalemia, dehydration, and hypotension; hypotension may be seen in the absence of antihypertensive medication. These symptoms should be monitored throughout the duration of the clinical trial both during Treatment and in the Follow-up period. If excessive GR and/or MR antagonism is suspected, patients should discontinue the study medication, and administration of intravenous fluids, and intravenous or oral hydrocortisone should begin without delay. [REDACTED]

[REDACTED] Symptoms should continue to be monitored even after the last dose of study medication in the follow-up period; intravenous fluids and hydrocortisone should be administered as clinically appropriate to reverse excessive GR and MR antagonism.

At each study visit starting with the Baseline visit, patients will be evaluated for signs and symptoms of excessive GR or MR antagonism. For patients who experience symptoms, the actions outlined in [Table 2](#) should be taken.

Guidelines for temporarily interrupting and restarting and for permanently discontinuing study treatment due to other safety events (hyperkalemia; hypotension; excessive miricorilant

exposure; suspected liver injury, and significant trauma, surgery, or medical illness) are outlined in [Table 2](#).

For assessment of suspected liver injuries, baseline values for ALT, AST and total bilirubin will be the mean of all values obtained from Screening through Day 1. Please refer to the laboratory manual or individual subject laboratory report for gender- and age-specific references.

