9.6 Prior and Concomitant Medications and Subsequent Therapies

Medications will be coded using the WHO Drug Global B3 version September 2019 or above. Medications entered on the eCRF will be mapped to ATC drug class (level 4) and generic drug name.

A prior medication is defined as any medication administered prior to the date of the first dose of study drug. A concomitant medication is defined as any medication administered on or after the date of the first dose of study drug and up to and including the last dose date. Medications newly administered after the last dose date are defined as subsequent therapies. A medication may be defined as more than one medication classification (prior, concomitant, or subsequent). The imputation rules for missing start and end date of a concomitant medication are described in [Section 12.1](#).

The proportion of patients who received prior, concomitant, and subsequent therapies or medications will be summarized separately for the Safety population. For all table summaries, the number and percentage of patients receiving any medication will be summarized by treatment group and overall. The preferred drug name and the preferred drug name within ATC drug class will be summarized separately and displayed by alphabetical order of ATC and descending order of incidence for the preferred drug name. Patients reporting use of more than one medication at each level of summarization (any medication received, ATC class, and preferred drug name) will be counted only once. The medication classification (e.g., prior, concomitant, subsequent, or a combination of classification) will be presented on the listing of prior, concomitant, and subsequent medications.

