12 APPENDIX

12.1 Imputation of Missing/Partially Missing Dates

For adverse events with a partial date, available date parts (year, month, and day) of the partial date will be compared with the corresponding date components of the start date and end date of the treatment-emergent period to determine if the event is treatment emergent. The following rules will be applied to impute partial dates for adverse events.

If start date of an adverse event is partially missing, following imputation rules will be applied:

- If both Month and Day are missing and Year = Year of treatment start date, then set to treatment start date.
- If both Month and Day are missing and Year \neq Year of treatment start date, then set to January 1.
- If Day is missing and Month and Year = Month and Year of treatment start date, then set to treatment start date.
- If Day is missing and Month and Year \neq Month and Year of treatment start date, then set to first of the month.
- If start date is completely missing, set to treatment start date as long as adverse event end date is not prior to treatment start date.

If end date of an adverse event is partially missing, following imputation rules will be applied:

- If both Month and Day are missing, then set to December 31.
- If only Day is missing, then set to last day of the month.
- If end date is completely missing, do not impute.

When the start date or end date of a medication is partially missing, the date will be imputed to determine whether the medication is prior or concomitant (or both). The following rules will be applied to impute partial dates for medications:

If start date of a medication is partially missing, following imputation rules will be applied:

- If both Month and Day are missing, then set to January 1.
- If only Day is missing, then set to the first.

If end date of a medication is partially missing, following imputation rules will be applied:

- If both Month and Day are missing, then set to December 31.
- If only Day is missing, then set to last day of the month.

If start date or end date of a medication is completely missing, no imputation is applied.

Certificate Of Completion

Envelope Id: E5A279FADB8040908649F2C5560E5C25
 Subject: Please DocuSign: CORT118335_860_SAP_v1_0_FINAL.docx.pdf
 Source Envelope:
 Document Pages: 27
 Certificate Pages: 5
 AutoNav: Enabled
 EnvelopeD Stamping: Disabled
 Time Zone: (UTC-08:00) Pacific Time (US & Canada)

Status: Completed

Envelope Originator:

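### The SAP 12.1 rules for partial medication dates ignore the dose dates, so some drugs started after the last dose are classed as concomitant and drop out of the subsequent-therapy table

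*SAP*

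**What the plan says.** SAP 9.6 defines three classes by the dose dates. Prior means given before first dose, and concomitant means given from first dose through last dose. For the third class, "Medications newly administered after the last dose date are defined as subsequent therapies". A drug may hold more than one class, the three are summarized separately in the Safety population, and missing dates are referred to SAP 12.1.

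SAP 12.1 gives these medication rules:

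- Partial start: "If only Day is missing, then set to the first"; "If both Month and Day are missing, then set to January 1".
- Partial end: "If only Day is missing, then set to last day of the month"; "If both Month and Day are missing, then set to December 31".
- Completely missing start or end: no imputation.

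The sentence that introduces them gives their purpose as deciding between prior, concomitant, or both. The subsequent class is not named. The adverse event rule in the same section does look at a dose date: "If Day is missing and Month and Year = Month and Year of treatment start date, then set to treatment start date".

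SAP 7.5 describes the imputation of these dates as conservative, without saying what that means for a medication. SAP 10, which lists changes from the protocol, does not touch the point.

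**The concern.** A class defined by first and last dose cannot be assigned reliably by a rule that looks at neither. Subsequent therapy is the most exposed class: a partial start is always moved to the earliest possible date, so in the last-dose month it always falls on or before last dose.

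SAP 9.8 says that the study was terminated because of safety observations. What patients newly needed after stopping drug is therefore of interest. Protocol 5.3.3 foresees treatment in the follow-up period: "intravenous fluids and hydrocortisone should be administered as clinically appropriate to reverse excessive GR and MR antagonism". A table of subsequent therapies that silently loses entries would understate such use, and the concomitant table would show it as use on study drug.

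There is a smaller effect around first dose. Protocol 4.2 requires that prohibited medications "must be discontinued at least 5 half-lives prior to a patient receiving their first study treatment". A drug stopped in the first-dose month, with the day of stopping unknown, is given a month-end stop date and is tabulated as concomitant as well as prior.

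**Working it through.** The documents give no figure to reproduce, so the check applies the SAP 12.1 rules and the SAP 9.6 definitions literally.

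**Worked example.** Assumed first dose 10 Mar 2021, last dose 12 Apr 2021, day missing from the date in question.

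| True date | Imputed date | True class | Class under 12.1 |
|---|---|---|---|
| Start 20 Apr | 1 Apr | subsequent | concomitant |
| Start 3 May | 1 May | subsequent | subsequent |
| End 4 Mar | 31 Mar | prior | prior + concomitant |
| End 20 Feb | 28 Feb | prior | prior |
| Start 20 Mar | 1 Mar | concomitant | prior + concomitant |
| Start 5 Apr | 1 Apr | concomitant | concomitant |

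The class is wrong only when the known month contains the relevant dose boundary. Only the first row loses its true class. If only the year 2021 is known, all six rows come out as prior + concomitant.

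**Starts after last dose.** Assume that last dose is equally likely on any of 365 days. A drug started d days later (d up to 28) is misfiled when both dates fall in the same month. For each d, 12d of the 365 last-dose dates push the start into the next month, so

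share misfiled = 1 − 12d/365.

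- d = 1 to 7 (mean 4): 1 − 48/365 = 0.868
- d = 1 to 28 (mean 14.5): 1 − 174/365 = 0.523
- d = 14 to 28 (mean 21): 1 − 252/365 = 0.310
- d = 28: 1 − 336/365 = 0.079
- Year only, d = 1 to 28: 1 − 14.5/365 = 0.960

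**Ends before first dose.** The same formula gives the share of washed-out drugs that gain concomitant.

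- d = 2: 1 − 24/365 = 0.934
- d = 7: 1 − 84/365 = 0.770
- d = 14: 1 − 168/365 = 0.540
- d = 28: 1 − 336/365 = 0.079

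**Starts on treatment.** Here a false prior class arises when start and first dose share a month and first dose is not on the 1st, so the share is 1 − 12d/365 − 12/365. For 28 days of treatment (d = 1 to 27, mean 14) this is 1 − 180/365 = 0.507. Full enumeration gives 0.250 for 56 days and 0.166 for 84 days. The concomitant class is kept in every case.

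**Would the adverse event rule be enough?** Applying that start rule to medications brings the false prior share to 0. The loss of subsequent therapies stays at 0.523, because the rule does not refer to last dose. End dates are not affected by it.

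**The case against.** The strongest defence is that earliest start with latest end gives the widest interval, so no possible use on study drug is missed. That is a fair reading of SAP 7.5, and it stands for the concomitant class. It does not justify removing a drug from the subsequent table, and the false prior class has no such rationale.

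It can also be said that 12.1 was written only for the prior and concomitant decision, and that nothing there says an imputed date cancels subsequent status. That makes the point a gap as much as an error. But 9.6 sends missing dates to 12.1, and no other rule for the third class exists.

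Partial dates may be rare. Concomitant medications are recorded at every visit (protocol Appendix A), the dosing diary asks for them (protocol 5.7), and queries are resolved before analysis (SAP 8.2). Year-only starts for drugs begun during the study are therefore unlikely, though the documents do not say so.

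Some stronger readings are tempting but not supported:

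- *All three errors replace the true class.* SAP 9.6 allows several classes, so around first dose a class is only added.
- *Compliant washouts become protocol deviations, or adverse event attribution shifts.* Deviations follow a separate specification document (SAP 9.3) and causality is judged by the investigator (protocol 8.10.2). Nothing derives either from imputed medication dates.
- *A drug with a completely missing start has no class.* A known end date can still settle it: an end before first dose gives prior, and an end between first and last dose gives concomitant.
- *Rescue hydrocortisone is generally lost from the subsequent table.* Treatment begun on the last-dose date is concomitant by definition, with no imputation involved. Only treatment begun later, in the same known month or year, is affected.

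**Conclusion.** The point holds as a minor defect. Three classes are defined by two dose dates, and the imputation rule refers to neither date and omits one class. Its one substantive consequence is that a drug started after last dose, with a partial start date whose known part contains the last dose, is reported as concomitant and is missing from the subsequent-therapy table.

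The size is about 52% of day-missing starts 1 to 28 days after last dose, falling from about 87% in the first week to about 8% at day 28. These are shares of affected records under uniformly spread dose dates. They are not estimates of how many entries in this trial are wrong, because the number of partial dates is not given.

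The false prior and concomitant classes around first dose are a secondary nuisance. The reach is limited to descriptive tables and listings: SAP 9.8 drops the protocol's efficacy analyses and SAP 9.9 makes no safety comparisons between groups.

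**What to change.** Change SAP 12.1 as follows.

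1. Add the subsequent class to the sentence that gives the purpose of the medication rules.
2. Partial start whose known parts match the month or year of last dose and do not exclude a start after it: count the drug as both concomitant and subsequent, and flag it as date-ambiguous in the listing. A known end date on or before last dose excludes the subsequent class.
3. Partial start or end whose known parts match the month or year of first dose: keep the conservative concomitant class, but flag the added prior or concomitant class as imputed. Use a known start or end date, or the Day 1 medication review (protocol 7.2) where recorded, to resolve it. The rule should not depend on the visit at which a drug was first entered, since the documents describe no such eCRF field.

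No true subsequent therapy with a partial start date is then lost. SAP 9.6 already allows several classes, so the table structure does not change.

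The cost is a few lines of text and programming, plus some drugs shown in two classes. For a patient dosed at least 28 days, a day-missing start on the last-dose date or up to 27 days before it gains a flagged subsequent class in 1 − (12 × 13.5 + 12)/365 = 0.523 of cases, unless a known end date rules it out. The flag makes that uncertainty visible. If the SAP is no longer open to change, SAP 1 provides for documenting the departure in the clinical study report.
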